### PROCEDURE:

Each patient will undergo RFA in a single session using ultrasonographic guidance. Therapeutic

guidance and diagnostic ultrasound will be performed with a 6- to 15-MHz probe attached to the GE Logiq E9 ultrasound system. The thyroid volume will be calculated using the formula for an ellipse (height x width x depth x  $\pi/6$ ) for each lobe and adding an additional volume of 1-2 cc for the isthmus, depending on its thickness. The percentage of volume reduction will be calculated as follows = [(initial volume - final volume) x 100%]/initial volume. All the patients will be sedated with general anesthesia during the procedure. General anesthesia will be used in light of the length of the procedure, the improved pain control, and the desire to avoid any motion interference that could compromise the accuracy of the technique. *A radiofrequency generator and an 18-gauge, 7-cm electrode with a 5mm, 7mm or 10mm active tip will be used. All radiofrequency procedures will be performed by 1 of 2 operators who are co-investigators in the trial and have extensive experience with this procedure. We will use an in-plane oblique approach for electrode placement as opposed to directly entering the thyroid parenchyma using the shortest pathway. The longer oblique pathway was chosen in order to lengthen the distance between the skin and the active tip of the RF electrode which reduces the chance of skin burns and allows a larger ablation diameter when needed by with the use of the pull-back technique. We will initially position the electrode in the deepest portion of the parenchyma, followed by more superficial placement. The approach is usually trans-isthmic, but to treat parenchyma in the upper portion of the thyroid, alternative oblique needle placements will be used to reach that area and to protect extrathyroidal structures from generated thermal energy.*

*To minimize the risk of complications, the outer approximately 5 mm of the parenchyma will not be treated, and the active tip of the electrode will be kept at a safe distance to prevent a skin burn. These safety measures will be the paramount concepts that will dictate the final approach to RFA. The ablation will employ the moving-shot technique as described elsewhere. The number of ablation cycles (number of times the RF generator is turned off to reposition the electrode to a new location in the parenchyma), total energy delivered, and total ablation times will differ according to target size. The target for the RFA will be the central area of the thyroid parenchyma, to minimize exposure to the thyroid capsule and thus limit the risk of side-effects to the surrounding structures. Within this area special attention will be dedicated to the regions with higher vascularity, if present, based on Doppler signal (particularly in AIT type 1.*

*The volume of thyroid parenchyma to be ablated will be expressed as a percent of the solid (non-cystic) thyroid volume based on the assumption that there is a linear correlation between thyroid volume and free thyroxine (FT4) levels and a gradual increase will be tested in the first 3 cases to decide the best approach for the rest of the series. Thus for example if the FT4 value is 2.4 ng/dL and we aim to normalize this parameter to 1.6 ng/dL we would target about 33% of the total thyroid parenchyma in order to decrease FT4 by 1/3. This calculated volume will be increased by 25% in case 2 and by 50% in case 3. These results will serve as basis for deciding the approach for the rest of the series. If these calculations lead to a planned ablation volume that would infringe on the safety parameters described above those safety parameters will prevail. Overall the planned ablation volume is a relative estimation of the actual ablation volume. The final volume will be dictated by the safety measures already described as well as by the specific anatomy of the thyroid in that particular patient. The procedure will be performed in the Radiology intervention area. We expect the intervention to last approximatively 45-60 minutes. Patients will be intensively monitored during RFA and then they will be observed for approximately 3 hours after the procedure in the PACU area and released home thereafter, unless adverse effects developed. We will look specifically for signs and symptoms of adverse effects of the intervention (e.g. pain, swelling, hoarseness, hypocalcemia, skin injury). If any such effects occur we will treat patients as appropriate (analgesia, skin care, respiratory support etc.). Hospitalization will be initiated if the patients' clinical situation requires it and the signs and/or symptoms do not resolve in the 3 hours of observation.*

In the first 48 hours post-procedure we will assess thyroid levels (TT3 and FT4) twice (once between 2 and 8 hours and again between 24 and 48 hours) and calcium level once between 24 and 48 hours. They will also have a brief clinical exam between 24-48h to assess procedure safety. In order to understand the bioactivity and the impact of thyroid hormone released during the procedure resting energy expenditure (REE) by indirect calorimetry will be assessed prior to RFA procedure and again 24 - 72h post RFA procedure; in addition, T3 and T4 research investigation will also be performed for that purpose; for this, separate blood draw for research will be done 48 hr prior to procedure and at E1 and E2 time points (see algorithm above) as well as measuring total T4 to have a better understanding if the measured hormone could be active hormone or a denatured chemical structure. The patients will then be monitored clinically at 2 and 4 weeks and biochemically at 1, 2 and 4 weeks, following thyroid levels and clinical signs and symptoms of thyrotoxicosis along with monitoring the procedure local area for signs and symptoms of adverse effects of the intervention (e.g. pain, swelling, hoarseness, hypocalcemia, skin injury). A final research evaluation will be performed at the time of the clinical follow-up between 3 and 6 months including thyroid values and a research thyroid ultrasound to assess parenchymal changes.

(Please refer to the overview of the study).

*The volume of thyroid parenchyma to be ablated is based on our assumption about linear correlation between serum thyroid hormone levels and total parenchymal volume. We will test this hypothesis and use the first 3 cases to decide if an adjustment to this approach is needed. We will present this data to Data Safety Monitoring Committee and propose modification to the protocol if necessary.*

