## Concomitant Interventions

### Allowed Interventions

*Medical therapy with steroids, antithyroid drugs or both will be ongoing peri-procedure with an increase in the ongoing anti-thyroid regimen the day of RFA and the day after the procedure after which pre-procedure doses will be resumed until thyroid levels are collected at the end of week 1 post-procedure. On a precautionary measure in the event of excess release of active T3 / T4 due to RFA, patients will be administered Lugols iodine solution (5 drops x 3 per day) starting after the procedure and continuing for the first 3 days post-RFA. Beta-blockers will be employed/increased starting 1 day before procedure and then adjusted in a manner analog with anti-thyroid regimen. These adjustments will be made in collaboration with cardiology, according to the cardiovascular status of the patient. If some of these changes are not clinically acceptable then bile-acid sequestrants will be used for their anti-thyroid effect, starting 2 days before procedure and continuing for 3 days after the procedure. If despite these interventions thyrotoxicosis will deteriorate post RFA both plasmapheresis and thyroidectomy will be discussed with the patient and pursued based on the clinical situation.*

*Of note – amiodarone can be continued during the study, at the discretion of the cardiologist consultant.*

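### The volume increases for cases 2 and 3 do not depend on how the preceding case turned out, and the first stated decision point comes after 3 of the 5 patients

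*Combined protocol and SAP*

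**What the plan says.** The PROCEDURE section bases the volume on an assumed linear relation between thyroid volume and FT4, and gives an example: to bring FT4 from 2.4 to 1.6 ng/dL, about 33% of the gland is targeted. It then states: "This calculated volume will be increased by 25% in case 2 and by 50% in case 3". On what follows: "These results will serve as basis for deciding the approach for the rest of the series". The end of the section says that the investigators will "use the first 3 cases to decide if an adjustment to this approach is needed", and will take those data to the Data Safety Monitoring Committee.

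Two kinds of protection are stated. One is anatomical: "the outer approximately 5 mm of the parenchyma will not be treated", and where the calculated volume would breach the safety limits, "those safety parameters will prevail". The other is medical, under Allowed Interventions: Lugol's solution, a temporary increase in antithyroid therapy, beta-blockade, and a rescue route: "If despite these interventions thyrotoxicosis will deteriorate post RFA both plasmapheresis and thyroidectomy will be discussed with the patient".

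Early data are already scheduled. Hormones are measured twice in the first 48 hours, with a brief safety exam at 24-48 hours. Patients are then "monitored clinically at 2 and 4 weeks and biochemically at 1, 2 and 4 weeks". After the short increase around the procedure, "pre-procedure doses will be resumed until thyroid levels are collected at the end of week 1 post-procedure".

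**The concern.** Followed as written, the rule gives case 2 or case 3 the larger multiplier even if the preceding patient was harmed or became more thyrotoxic. Cases 4 and 5 have stated protection from what was learned earlier. Cases 2 and 3 have none.

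This matters because the Rationale calls this the first study of RFA in AIT, in patients who are usually very sick with cardiac disease. The reassurance offered there (no worsening in 47 treated toxic nodules or goiters) is indirect, since those patients did not have AIT. The plan itself provides against excess hormone release caused by the procedure, and the linear assumption behind the volume rule is one of the things being tested.

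**Working it through.** **Inputs from the protocol.** 5 patients; decision after 3; FT4 2.4 to 1.6 ng/dL; multipliers 1, 1.25 and 1.5; outer rim of about 5 mm untreated; 12-18 months to complete; 10-15 qualifying cases a year.

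**Assumptions, not in the protocol.** Equal ellipsoid lobes of 5x2x2, 6x3x3 or 7x4x4 cm, isthmus ignored; FT4 values of 2.0 and 3.2; arrival patterns. Each multiplier is read as applying to that patient's own calculated volume.

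1. *The plan's figure.* (2.4 - 1.6)/2.4 = 33.3%, which reproduces the stated 33%.

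2. *Planned steps at the same FT4.* 33.3% x 1.25 = 41.7%; 33.3% x 1.5 = 50.0%.

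3. *Patients treated before the decision.* 3/5 = 60%.

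4. *Cap from the rim.* Taking 0.5 cm off each side leaves the product of (d - 1)/d over the three dimensions:
   - 5x2x2 cm: 4/5 x 1/2 x 1/2 = 20.0%
   - 6x3x3 cm: 5/6 x 2/3 x 2/3 = 37.0%
   - 7x4x4 cm: 6/7 x 3/4 x 3/4 = 48.2%

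5. *Share treatable in cases 1/2/3,* the smaller of planned share and cap:

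| FT4 | 5x2x2 cm | 6x3x3 cm | 7x4x4 cm |
|---|---|---|---|
| 2.0 (base 20%) | 20/20/20% | 20/25/30% | 20/25/30% |
| 2.4 (base 33%) | 20/20/20% | 33/37/37% | 33/42/48% |
| 3.2 (base 50%) | 20/20/20% | 37/37/37% | 48/48/48% |

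6. *FT4 from which the multiplier changes nothing.* Case 1 already reaches the cap when (FT4 - 1.6)/FT4 = cap, so FT4 = 1.6/(1 - cap): 1.6/0.800 = 2.0; 1.6/0.630 = 2.5; 1.6/0.518 = 3.1.

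7. *Different baselines.* Case 1 at FT4 2.4 is planned at 33%. Case 3 at FT4 2.0 is planned at 20% x 1.5 = 30%, which is less despite the higher multiplier.

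8. *Chance that a week-1 condition defers at least one of the two steps.* This needs one of two gaps between cases to be under g = 1 week, with 5 arrivals over T weeks.
   - Even spacing: T/5 = 10.4 weeks (T = 52) or 15.6 weeks (T = 78), so 0%.
   - Uniform arrival times, 1 - (1 - 2g/T)^5: 17.8% (T = 52), 12.2% (T = 78).
   - Poisson arrivals, 1 - exp(-2g x 5/T): 17.5% and 12.0%.
   - A week-4 condition (g = 4) would give 56.6% and 41.8% (uniform) or 53.7% and 40.1% (Poisson).

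   If accrual took only 6 months, because the 12 months include 6 months of follow-up, the week-1 figure would be 32-33%. That needs 5 of the 5-7.5 patients qualifying in 6 months to accept, or 67-100%.

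**The case against.** The strongest reply is that little turns on this in practice. One site and two operators treat everyone. Five patients over 12-18 months arrive about 10-16 weeks apart on average, so 4-week data would often be in hand, and the investigators would be likely to react to a bad case. The safety measures override the calculated volume, and in small glands, or at high FT4, the multiplier does nothing. This stands as an argument about size. It makes a condition easy to meet, but does not supply one.

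A second reply is that a between-case rule may exist elsewhere. The opening pages and the overview figure are not available, and no committee charter is among the documents. This also stands, so the point is confined to the available text.

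A third is that week 1 is an imperfect gate. The STUDY DESIGN section sets a 4-week response window and a first-month safety window, and week-1 values follow three days of Lugol's and two days of raised antithyroid therapy. Gating the multiplier also does not stop a next patient with a higher FT4 from having a larger ablation. All of this is true. Week 1 is nevertheless the last planned reading before the background doses may change, and a mandatory 4-week wait would defer far more steps.

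**Conclusion.** The point holds as a gap in the escalation rule. Two of five patients are assigned a higher multiplier without regard to the preceding outcome, and 3 of 5 are treated before the first stated decision. It is a cheap safety improvement, not a flaw that invalidates the study.

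Several stronger readings are tempting and are not supported:

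- *The escalation is unlimited.* It is not: the anatomical limits prevail over the calculation.
- *Case 3 will have the largest ablation.* It need not, because each volume starts from that patient's own FT4 and is capped by that patient's gland.
- *Patients are unprotected.* Each treated patient has precautions, monitoring and rescue. What is missing is a stated way for one patient's result to affect the next patient's multiplier before case 4.
- *A probability of harm can be given.* The documents offer no basis for one.
- *The 80% rule under Adherence Assessment gives a range for the delivered volume.* It does not, because the intended volume there may mean the volume after the safety limits are applied.

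The caps and FT4 thresholds depend on the assumed lobe shapes, and the deferral figures on the assumed arrival patterns. The 60% depends on neither.

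**What to change.** Add to the PROCEDURE section, after the escalation rule and again where the first 3 cases are discussed:

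> The +25% (case 2) and +50% (case 3) are applied only after the preceding case's scheduled hormone values and adverse events, through at least week 1 plus all later data then available, have been reviewed. If they show a procedure-related serious adverse event or worsening thyrotoxicosis, the multiplier is not raised. After such a serious event no further patient is treated until the Data Safety Monitoring Committee has reviewed it. If a patient must be treated before the week-1 data exist and no serious event has occurred, the multiplier is no higher than the previous one.

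What counts as worsening is a clinical decision for the investigators and the committee, and is best agreed before case 1.

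The cost is two short reviews of data the plan already collects. No patient waits for week-1 data unless a serious event has occurred; after one, the next patient may wait for the committee. A step may be deferred when cases arrive close together: 0% if evenly spaced, about 12-18% if random over 12-18 months. Effects that appear after week 1 may still be missed when the next case comes early.

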**Rationale:**

RFA has been used for the management of thyroid nodules for more than a decade . We have employed it here at Mayo Clinic for the past 4 years with good results . While mainly used for non-toxic thyroid nodules there is encouraging data describing the response to RFA in the case of toxic thyroid adenomas. In total in the literature there are 47 cases of toxic nodules or toxic goiters that were treated with RFA (8-10) and in 50% of these cases the thyroid function normalized and in none of them did thyrotoxicosis worsened as a result of therapy. RFA has the capacity to lead to destruction of thyroid parenchyma and also to denaturation of stored thyroid hormone. Thus it seems to provide the perfect approach to target both mechanisms of AIT in an expeditious manner which is essential in these usually very sick individuals with coexistent cardiac co-morbidities. So far there is no reported data on the efficacy of RFA in AIT and this would be the first study on this therapy, hence our pilot study approach.

[figure not shown]

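### The multiplier on planned ablation volume steps up at cases 2 and 3 by case number, with no stated link to the earlier case's safety outcome

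*Combined protocol and SAP*

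**What the plan says.** All places are in the combined protocol and SAP.

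- **Base volume and increase (Procedure).** The planned volume is a share of the solid thyroid volume, proportional to the fall in FT4 that is wanted. Then: "This calculated volume will be increased by 25% in case 2 and by 50% in case 3". The results of these cases are to guide the rest of the series.
- **Limits (Procedure).** The outer 5 mm or so of the gland is left untreated and the electrode tip is kept away from the skin. "If these calculations lead to a planned ablation volume that would infringe on the safety parameters described above those safety parameters will prevail". Anatomy also governs the final volume.
- **Response to harm.** Under Procedure, adverse effects lead to treatment, and to admission if they do not settle during the 3-hour observation. Under Allowed Interventions: "If despite these interventions thyrotoxicosis will deteriorate post RFA both plasmapheresis and thyroidectomy will be discussed with the patient". Both concern the affected patient.
- **Safety data (Procedure).** Hormone levels are taken twice in the first 48 hours. Calcium and a brief examination follow at 24 to 48 hours. After that: "The patients will then be monitored clinically at 2 and 4 weeks".
- **Committee (Procedure).** The first three cases are used to judge whether the assumed link between gland volume and hormone level needs adjusting. "We will present this data to Data Safety Monitoring Committee and propose modification to the protocol if necessary".
- **Novelty (Rationale).** "So far there is no reported data on the efficacy of RFA in AIT and this would be the first study on this therapy".

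**The concern.** Safety is part of the hypothesis, and Study Design makes it the secondary objective over the first month. The protocol takes systemic harm seriously: it gives iodine solution in case the procedure releases active hormone, and it measures energy expenditure and total T4 because the activity of released hormone is uncertain. Whether harm grows with ablated volume is therefore open when case 1 is treated, yet the multiplier for cases 2 and 3 is already fixed.

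The safety observations that could inform each step are collected, but the supplied text does not connect them to it. If case 1 or 2 ended in a life-threatening event or an emergency thyroidectomy, a team following the text exactly could treat the next patient at the higher multiplier without outside review.

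Attribution makes this harder. Background reports more hospitalisation, heart failure and arrhythmia in this group, and inclusion criterion B admits patients hospitalised with heart failure or haemodynamic instability. The treating team could reasonably put an event down to underlying disease, so a trigger should not rest on its judgement alone.

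**Working it through.** **1. The plan's own figure.** Inputs from Procedure: FT4 2.4 ng/dL, target 1.6 ng/dL.

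Base share = (FT4 − target) / FT4 = (2.4 − 1.6) / 2.4 = 33.3%. This matches the stated figure of about 33%.

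**2. Apply the multipliers, before the limits.** The first row is the protocol's example. The other FT4 values are assumptions, with the target kept at 1.6.

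| FT4 (ng/dL) | Case 1 (×1.00) | Case 2 (×1.25) | Case 3 (×1.50) |
|---|---|---|---|
| 2.4 | 33.3% | 41.7% | 50.0% |
| 3.2 | 50.0% | 62.5% | 75.0% |
| 4.0 | 60.0% | 75.0% | 90.0% |
| 4.8 | 66.7% | 83.3% | 100.0% |

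At FT4 4.8 the case 3 plan reaches the whole gland, so the procedural limits alone would hold it back.

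**3. Does volume rise from one patient to the next?** Not necessarily. The case 1 FT4 that gives the same plan as a case 2 at 2.4 is 1.6 / (1 − 0.4167) = 2.74 ng/dL. Above that, case 1 is planned larger. With an assumed case 1 FT4 of 4.0, the plans are 60% and then 42%. Only the multiplier follows case number.

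**4. Steps affected.** Five patients give four between-case steps. Two of them (1 to 2, and 2 to 3) carry a prescribed increase, and no committee contact is stated before either. Later steps also lack a stated event trigger, but no increase is prescribed there, so that is minor.

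**5. What is known about harm.** Rationale cites 47 toxic nodule or goiter cases and says that "in none of them did thyrotoxicosis worsened as a result of therapy". For 0/47 the one-sided 95% upper limit is 1 − 0.05^(1/47) = 6.2%. This is a different population and one type of harm, so it gives no rate for RFA in AIT.

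**6. How often would a hold rule fire?** The per-patient trigger rates below are assumptions, used only to gauge the burden. Chance of at least one trigger in n patients = 1 − (1 − p)^n.

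| Assumed p | Before case 2 (n = 1) | Before case 3 (n = 2) | Before case 5 (n = 4) |
|---|---|---|---|
| 5% | 5% | 9.8% | 18.5% |
| 10% | 10% | 19% | 34% |
| 20% | 20% | 36% | 59% |
| 50% | 50% | 75% | 94% |

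A broad trigger with a high p would stop the trial often. This argues for a narrow list.

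**7. Spacing.** Study Design expects completion in 12 to 18 months, with each patient in the trial for 4 to 6. If completion includes the last patient's follow-up and case 1 falls at the start (assumptions), the average gap lies between (12 − 6) / 4 = 1.5 and (18 − 4) / 4 = 3.5 months. That is longer than the one-month safety window on average, but the supplied text sets no minimum gap.

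**The case against.** The strongest reply is that this rests on silence. The protocol names a committee, and event-triggered review would ordinarily sit in its charter, which is not supplied. The overview figure, to which Procedure refers, is also missing. This stands. A reader might infer that the trial has no event-triggered oversight at all, and the documents do not support that. The point is limited to what the supplied text states.

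A reader might also infer that each patient is ablated more than the one before. Step 3 shows that this does not follow, and the limits and anatomy govern the final volume.

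Third, practical exposure is modest: five patients at one centre, two operators who are both co-investigators, and gaps that would usually let one patient's month of safety data be seen before the next procedure. An ad hoc halt remains possible. This lowers the stakes, but it does not make the halt required or recorded.

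Fourth, the documents do not show that harms such as hoarseness depend on ablated volume, and the untreated rim applies in every case. That is fair, and the remedy is partly a general halting rule. Dependence on volume is, however, untested rather than excluded.

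Finally, a rule triggered by any unplanned or prolonged hospital stay would be too broad. This group is selected partly for cardiac admissions, no planned stay is given against which to judge prolongation, and a hold could delay a criterion B patient with few alternatives. This stands too, and it shapes the fix.

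**Conclusion.** The point holds in a limited form. The supplied text raises the multiplier to 1.25 and then 1.50 by case number, before the procedural limits, and states no rule tying either step to the earlier patient's safety outcome. The stated committee contact draws on the first three cases together, addresses the dosing assumption, and is not prompted by an event.

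The size is two of four steps, and at the protocol's example FT4 a plan that goes from 33% to 42% to 50% of the gland. The text permits escalation after a serious harm. It does not require it, and nothing shows that the team would do it. No probability of harm can be drawn from the documents.

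This is a cheap improvement to patient safety in a first study of the therapy. It falls away if the charter or overview figure already requires review before the next case.

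**What to change.** First confirm whether the committee charter or the overview figure already requires event-triggered review. If not, add to Procedure, beside the escalation rule:

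> *If, within one month of RFA, a treated patient dies; has a life-threatening event or ICU transfer; has deterioration of thyrotoxicosis leading to plasmapheresis or thyroidectomy; or, if an outpatient, is admitted because of adverse effects instead of being released after the 3-hour observation, then the multiplier is not increased and no further patient undergoes RFA until the Data Safety Monitoring Committee has reviewed the event, whatever the treating team's attribution, and recorded continue, modify or stop. Voice change persisting at 4 weeks, or a later admission, is reported to the committee before the next increase, but does not by itself prevent treatment of a patient at the unincreased calculated volume.*

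The second sentence keeps common or hard-to-attribute events from stopping treatment, while still putting them before the committee ahead of an increase.

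**Cost.** A short added paragraph and, if needed, an ad hoc review by the committee already named. No new visits, tests or patients.

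**Downside.** A possible short pause that may prove unnecessary and could delay a waiting criterion B patient. No minimum interval between cases is proposed, because such patients may be unable to wait. Events late in the one-month window may therefore be missed if cases are closely spaced.

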#### **Biospecimens – Categories 2 and 3**

(2) Collection of blood samples. When multiple groups are involved copy and paste the appropriate section below for example repeat section b when drawing blood from children and adults with cancer.

- a. **From healthy, non-pregnant, adult subjects who weigh at least 110 pounds.** For a minimal risk application, the amount of blood drawn from these subjects may not exceed 550ml in an 8 week period and collection may not occur more frequently than 2 times per week.

Blood samples will be obtained; Volume10 cc per clinical visit and 10 cc for research (3 time points)

- b. **From other adults and children considering age, weight, and health of subject.** For a minimal risk application, the amount of blood drawn from these subjects may not exceed the lesser of 50 ml or 3 ml per kg in an 8 week period, and collection may not occur more frequently than 2 times per week.

No blood samples will be obtained.

(3) Prospective collection of biological specimens other than blood: NONE

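### The only research hormone baseline described is drawn 48 hours before RFA, so a release at ablation could look smaller than it is; a tube just before ablation is a cheap improvement.

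*Combined protocol and SAP*

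**What the plan says.** All references are to the combined protocol and SAP.

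- **Purpose (PROCEDURE).** The extra measurements are made "In order to understand the bioactivity and the impact of thyroid hormone released during the procedure". Total T4 is added to help tell active hormone from a denatured form.
- **Research draws (PROCEDURE).** A "separate blood draw for research will be done 48 hr prior to procedure and at E1 and E2 time points". E1 and E2 are defined in a figure that is not shown.
- **Number of draws (Biospecimens – Categories 2 and 3).** The volume is "10 cc for research (3 time points"), listed separately from the blood taken at clinical visits.
- **Early post-procedure thyroid levels (PROCEDURE).** TT3 and FT4 are measured "once between 2 and 8 hours and again between 24 and 48 hours".
- **Drug changes around the procedure (Allowed Interventions).** Steroids, antithyroid drugs or both continue, "with an increase in the ongoing anti-thyroid regimen the day of RFA and the day after the procedure". "Beta-blockers will be employed/increased starting 1 day before procedure". Lugol's solution starts after RFA and runs for three days. If some of these changes are not clinically acceptable, bile-acid sequestrants are used for their anti-thyroid effect, "starting 2 days before procedure and continuing for 3 days after the procedure".
- **Analysis (STUDY DESIGN; Data Analysis Plan).** Five patients, a historical control group, and descriptive statistics only.

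**The concern.** An acute release is a step at the moment of ablation. The natural way to see it is to compare a sample just before with samples soon after. Here the before sample is two days old, and every listed drug change starts at or after it. Any fall in hormone level between that sample and ablation is subtracted from the apparent release. The error would be on the reassuring side, and the protocol itself treats excess release as a risk, since that is its stated reason for giving Lugol's solution. With five patients and no concurrent control, nothing in the planned analysis could separate drift before the procedure from release during it.

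**Working it through.** There is no figure in the plan to reproduce: the Data Analysis Plan gives no sample-size or precision calculation. The check compares timings and then shows how a fall before RFA would act.

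**1. Count of baselines.** The three research time points are used up by the 48-hour draw, E1 and E2. The visible text describes no research sample just before ablation.

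**2. Share of each interval that lies before RFA.** Assumption: E1 is the 2–8 h sample and E2 the 24–48 h sample. For a sample t hours after RFA, the share is 48/(48 + t).

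| Sample | t (h) | Baseline to sample (h) | Share before RFA |
|---|---|---|---|
| E1, earliest | 2 | 50 | 48/50 = 96% |
| E1, latest | 8 | 56 | 48/56 = 86% |
| E2, earliest | 24 | 72 | 48/72 = 67% |
| E2, latest | 48 | 96 | 48/96 = 50% |

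**3. What changes in those intervals (Allowed Interventions).**

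| Treatment | Start | Would a sample just before ablation take out its effect up to then? |
|---|---|---|
| Ongoing steroid and/or antithyroid therapy | already running | Yes |
| Bile-acid sequestrants (fallback only) | day −2 | Yes |
| Beta-blocker change | day −1 | Yes, but the documents credit it with no effect on hormone level |
| Increase in anti-thyroid regimen | day 0 | Not the effect after the sample |
| Lugol's solution | after RFA | No |

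**4. How much a fall before RFA would hide.** Let d be the fractional fall from the 48-hour sample to ablation, and r the rise caused by release, as a fraction of the level just before ablation. With no other effect, the change seen from the 48-hour value is (1 + r)(1 − d) − 1. This is zero or negative when r ≤ d/(1 − d). The documents give neither d nor r, so d is assumed. The last column uses the protocol's worked example of FT4 2.4 ng/dL as the 48-hour value, where the hidden amount is 2.4 × d.

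| Assumed d | Release fully hidden up to d/(1 − d) | Hidden amount (ng/dL) |
|---|---|---|
| 0% | 0% | 0 |
| 4% | 0.04/0.96 = 4.2% | 0.10 |
| 5% | 0.05/0.95 = 5.3% | 0.12 |
| 10% | 0.10/0.90 = 11.1% | 0.24 |

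**5. Is any value of d suggested by the documents?** Only indirectly. One limb of inclusion criterion B is a T4 decrease of less than 25% after two weeks of standard therapy. At a constant proportional rate, a 25% fall in 14 days is 1 − 0.75^(2/14) = 4% in 2 days. That is a ceiling for patients who enter on that limb, provided their earlier rate continues. It is not an expected trend, and it does not bound patients who enter by other routes or who start a sequestrant.

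**6. What a day-0 baseline would and would not remove.** Assume r = 10% and d = 10%.

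- From the 48-hour value: 1.10 × 0.90 − 1 = −1.0%.
- From a sample just before ablation: +10.0%.

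Now let drugs started on day 0 or later lower the level by an assumed further 5%.

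- From the 48-hour value: 1.10 × 0.90 × 0.95 − 1 = −5.95%, about −6%.
- From a sample just before ablation: 1.10 × 0.95 − 1 = +4.5%.

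The later baseline removes the part before the procedure and leaves the part after it.

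**The case against.** The case for leaving the plan alone has several good points.

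- **The documented drug effect before day 0 is thin.** Among changes that start before the day of RFA, only the sequestrants are credited with an anti-thyroid effect, and they are a fallback. This stands. In other patients the remaining source before the procedure is ongoing therapy, whose effect over two days may be small.
- **No change score is defined.** The plan speaks of bioactivity and impact, and whether hormone is active or denatured is partly a question within a single sample. This stands in part. Hormone released during the procedure still calls for a before-and-after comparison.
- **The missing figure may show a clinical sample on the day.** This cannot be excluded. It would supply routine thyroid levels, but it would not be one of the three research draws.
- **Safety does not rest on this contrast.** Absolute FT4 and TT3, calcium, a clinical exam at 24–48 h, adverse-effect monitoring and resting energy expenditure are all planned. This stands, and it keeps the point minor.

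A reader might also infer that E1 timing depends on whether the patient had an adverse effect, because uncomplicated patients are "observed for approximately 3 hours after the procedure in the PACU area and released home thereafter" while the window runs to 8 h. The documents do not support that. STUDY DESIGN also recruits inpatients, who can be sampled late without any adverse effect, and nothing says that outpatients cannot be sampled after they leave. Nor do the documents give a time course of release that would favour one fixed E1 time. What remains is a wide window, for which recording the actual time is enough.

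**Conclusion.** The point holds as a minor one. In the visible text the only research baseline is two days before ablation, and most of the interval to E1, and at least half of the interval to E2, lies before RFA. A fall in that time could make a release look smaller than it is. The size is unknown: about 4% hidden for an assumed 4% fall, 11% for an assumed 10% fall, and nothing if levels are steady.

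This rests on three assumptions: that E1 and E2 are the 2–8 h and 24–48 h samples, that the figure not shown adds no research baseline, and that release will be judged against the 48-hour value.

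Two stronger readings should be avoided. One is that drug effects will hide a release; the documents support only that a fall before RFA could do so. The other is that a later baseline would isolate the effect of RFA. It would not, because the day-0 regimen increase and Lugol's solution still overlap E1 and E2.

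**What to change.** - Take the research baseline (FT4, TT3, total T4 and the T3/T4 research tube) on the day of RFA, just before ablation. If the 48-hour draw is needed for other reasons, keep it, add a day-0 tube, and compute the E1 and E2 changes from day 0.
- Record the actual time of every sample and the start time of each drug change, including whether a sequestrant was given.
- State in the Data Analysis Plan that changes at E1 and E2 reflect RFA together with the day-0 regimen increase and Lugol's solution.

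No change to any treatment is implied. Moving the draw adds no blood and no further sample. Keeping both adds one tube, about 10 mL if the 10 cc in the Biospecimens section is per time point, and that section's count would rise from three to four. The change has to be made before a patient is treated, because a missing day-0 sample cannot be recovered later.
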